9.8.5 IMMUNOGENICITY ASSESSMENTS

Immunogenicity assessments will be analyzed descriptively using the following categories based on SAS:

- Number (%) of subjects with an ADA-positive sample at baseline and at post-baseline. Percentages will be calculated based on the number of subjects assessed with a determinant baseline ADA sample or at least one determinant post-baseline ADA sample, respectively.
- Number (%) of subjects with an ADA-positive sample cross-reactive to endogenous GLP-2 at baseline and at post-baseline. Percentages will be calculated based on the number of subjects assessed with a determinant baseline ADA sample or at least one determinant post-baseline ADA sample, respectively.
- Number (%) of subjects with a neutralizing antibody (nAb)-positive sample at baseline or at post-baseline. Percentages will be calculated based on the number of subjects assessed with a determinant baseline nAb sample or at least one determinant post-baseline nAb sample, respectively.
- Number (%) of subjects with a nAb-positive sample cross-reactive to endogenous GLP-2 at baseline and post-baseline. Percentages will be calculated based on the number of subjects assessed with a determinant baseline nAb sample or at least one determinant post-baseline nAb sample, respectively.

The above analyses will be performed based on availability of immunogenicity assessment data.

All immunogenicity assessment data will be listed.

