7.6.4 Immunogenicity Analysis

All immunogenicity analyses will be descriptive and carried out with a special focus on neutralizing antibodies and treatment-induced or treatment-boosted ADA anti-apraglutide. The impact on PK, PD, and safety will be described.

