10. DEVIATIONS FROM ANALYSIS DESCRIBED IN THE PROTOCOL

The following update has been made from the planned analysis defined in the protocol to align the safety analysis plan as defined in the TA799-007 study.

- In the protocol, TEAE is defined as all AEs occurring after first dose of trial medication and up to the 4 weeks follow-up visit. However, for the safety analysis, TEAE will be defined as any adverse events that started on or after the first dose of trial medication (i.e. no longer depends on 4 weeks follow-up visit).

There is one deviation from the planned analysis described in the protocol. According to the protocol, the primary endpoint AESIs are to be derived based on SMQ or CQs. Sponsor issued NTF (See [Appendix 4: Addendum to Statistical Analysis Plan](#)), to clarify that AESI will be identified by using the investigator's assessment, reported in eCRF for analysis.

In addition, the following list contains typographical error (typo) corrections from the protocol that have been made to this SAP for clarity:

- The protocol refers to 'change in absolute absorption'. It is clarified in SAP that this refers to 'absolute change from baseline' in comparison to 'relative change in absorption'. Note: This SAP uses 'absolute change from baseline' and 'change from baseline' interchangeably.
- One of the secondary efficacy endpoints defined in the protocol is 'clinical responder at Week 52' but unlike the protocol synopsis and Section 1.5.2.2 of the protocol, Section 7.1.2 of the protocol indicated Week 48 instead of Week 52. This typo has been corrected to Week 52 in this SAP.
- One of the efficacy endpoints defined in the protocol is 'change in dietary intake of wet weight, energy, macronutrients, fluid, electrolytes (sodium, potassium, calcium, and magnesium) from baseline at Week 4 and Week 48', but this 'fluid' is a part of weight as oral fluid; hence, this text, 'fluid', is omitted in this SAP.
- One of the efficacy endpoints defined in the protocol is "change in fecal excretion of wet weight, energy, macronutrients, fluid and electrolytes (sodium, potassium, calcium, and magnesium) from baseline at Week 4 and Week 48", but this "fluid" is a part of wet weight (urine), which has already been covered by urine output as a part of the secondary efficacy endpoint; hence, the text, 'fluid', is omitted in this SAP.

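### SAP 9.8.5 tabulates only any-positive antibody counts; the induced/boosted classification and the description of ADA impact in Protocol 7.6.4 are missing, and Section 10 does not declare the change

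*SAP*

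**What the plan says.** **Protocol.** Section 7.6.4 makes the immunogenicity analysis descriptive, with a "special focus on neutralizing antibodies and treatment-induced or treatment-boosted ADA anti-apraglutide". It adds: "The impact on PK, PD, and safety will be described". It sets no denominator, titer rule or table layout.

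**SAP.** Section 9.8.5 gives four summaries on the Safety Analysis Set. The first is "Number (%) of subjects with an ADA-positive sample at baseline and at post-baseline". The third is "Number (%) of subjects with a neutralizing antibody (nAb)-positive sample at baseline or at post-baseline". The other two repeat these for samples cross-reactive to endogenous GLP-2. For ADA the denominator rule is: "Percentages will be calculated based on the number of subjects assessed with a determinant baseline ADA sample or at least one determinant post-baseline ADA sample," so each count has its own base; the nAb rule has the same form. The section closes with "All immunogenicity assessment data will be listed". Section 9.8.6 summarizes apraglutide concentrations and citrulline by scheduled visit and leaves exploratory PK and PK/PD work to another document.

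**Status of ADA.** Under protocol version 4, which SAP Section 2 applies to all subjects, ADA is a component of the primary endpoint (SAP 7.1).

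**Declared changes.** SAP Section 10 records a revised TEAE definition, then says "There is one deviation from the planned analysis described in the protocol" (how AESIs are identified), then lists wording corrections. None concerns immunogenicity.

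**The concern.** A subject who enters with antibodies and simply keeps them is counted in the post-baseline rate although the drug induced nothing. Such a subject can enrol: exclusion criterion 19 (Protocol 3.2.2) bars only known neutralizing antibodies, and criterion 17 bars only treatment of more than 2 weeks with GLP-2 analogs and related agents in the 6 months before Screening. Protocol 4.7.1 itself says that earlier use of such agents may affect ADA production.

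The SAP separates new from existing findings for other parts of the same primary endpoint. Adverse events are split into pre-treatment and treatment-emergent (9.8.2), and laboratory panels get baseline-to-worst shift tables (9.8.3). ADA gets neither.

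At stake is whether the tables can answer the question the protocol poses: how many subjects developed or increased antibodies on apraglutide, and whether this affected exposure, response or safety. Protocol 1.7.2 reports low-titer ADA in five subjects of earlier trials without saying whether they were present before dosing, and says they had no apparent effect on PK or PD. The matching description for this trial has no visible place in the SAP.

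**Working it through.** The plan states no figure to reproduce. The check is a comparison of text, then an illustration of size.

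**1. Protocol element against SAP provision**

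| Protocol 7.6.4 | SAP |
|---|---|
| Focus on neutralizing antibodies | Kept in 9.8.5, as any-positive counts |
| Treatment-induced ADA | No category |
| Treatment-boosted ADA | No category and no titer rule |
| Impact on PK and PD | No summary by ADA status in 9.8.5 or 9.8.6 |
| Impact on safety | No summary by ADA status in 9.8.2 or 9.8.5 |
| Declared as a change | Not in Section 10 |

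**2. Inputs for the illustration**
- Subjects: 2 + 7 = 9 enrolled (SAP Section 2). *Assumption:* all 9 were treated and have usable baseline and post-baseline samples.
- *b* = baseline-positive subjects who stay positive without boosting; *i* = treatment-induced subjects. *Assumptions:* the documents give neither number, and there are no other baseline-positive subjects.

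**3. Formulas**
- SAP post-baseline rate = (b + i)/9
- Treatment-emergent rate among all subjects = i/9
- Induced rate among baseline-negatives = i/(9 − b)
- Excess of the SAP rate over the treatment-emergent rate = b/9, or 1/9 = 11.1 points per such subject

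**4. Results**

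| b | i | SAP post-baseline | Treatment-emergent, all subjects | Induced, baseline-negatives |
|---|---|---|---|---|
| 0 | 1 | 1/9 = 11.1% | 1/9 = 11.1% | 1/9 = 11.1% |
| 1 | 0 | 1/9 = 11.1% | 0/9 = 0% | 0/8 = 0% |
| 1 | 1 | 2/9 = 22.2% | 1/9 = 11.1% | 1/8 = 12.5% |
| 2 | 1 | 3/9 = 33.3% | 1/9 = 11.1% | 1/7 = 14.3% |

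**5. Can the two planned counts be subtracted to recover the induced number?** No. Suppose the table shows 1/9 positive at baseline and 2/9 post-baseline. If the baseline-positive subject stayed positive, one of 8 baseline-negatives was induced (12.5%). If that subject had no positive sample after dosing, two of 8 were induced (2/8 = 25.0%). The planned table is the same in both cases.

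**6. How likely is at least one baseline-positive subject?** The chance is 1 − (1 − p)^9 for baseline prevalence p. For assumed p of 2%, 5%, 10% and 20% it is 16.6%, 37.0%, 61.3% and 86.6%. These are chances of baseline positivity, not of persistence, which the excess also requires.

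**The case against.** The strongest reply is that little is lost in a trial of this size. SAP 9.8.5 lists all immunogenicity data, and SAP 9.1 lists all data by subject and date. Concentrations, citrulline and adverse events are listed too, so a reader can trace nine subjects by hand. The SAP shows baseline and post-baseline positivity together, names each denominator and never calls the post-baseline figure treatment-induced. The protocol commitment is descriptive, and a narrative in the trial report might meet the impact sentence. The SAP also keeps the neutralizing-antibody focus and adds cross-reactivity to endogenous GLP-2, which Protocol 7.6.4 does not request.

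Much of this stands, and it rules out four stronger readings:
- *That the post-baseline rate is inflated.* This depends on a baseline-positive subject staying positive, and no baseline prevalence is given.
- *That the within-subject transition is lost.* It is missing from the planned tables but recoverable from the listings.
- *That a boosted response cannot be seen.* Protocol 5.1.11.1 describes testing for antibodies and their neutralizing capacity without mentioning titers. If titers exist, the listing should show them; if not, no boosting rule can be applied.
- *That no impact analysis exists anywhere.* The note to file, the mock-up shells and the separate PK/PD document are not available. SAP Sections 2, 6, 8, 9.8.2 and 10 point to the addendum and 9.8.5 does not, which leaves the matter open.

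What the reply does not supply is a pre-specified definition or denominator for induced antibodies, or a record in Section 10 that the protocol's classification was left out. A listing does neither.

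**Conclusion.** The gap between Protocol 7.6.4 and SAP 9.8.5 is real and undeclared, and it concerns a primary endpoint component. The planned tables measure how many subjects were ever positive at baseline and after dosing; they do not measure treatment-emergent antibodies.

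The numerical effect is conditional: 11.1 points per subject who is positive at baseline and persists without boosting, and zero if there is none. It rests on all 9 enrolled subjects being evaluable; SAP 9.4 allows for subjects enrolled but not treated, so the denominator could be smaller. In the example with one pre-existing and one induced case, the like-for-like comparison is 22.2% against 11.1% of all subjects. The 12.5% figure has a different denominator, so the 9.7-point difference from 22.2% should not be read as the per-subject effect.

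The conclusion is subject to the note to file of 6 December 2022. It is a correction worth making, not an error that invalidates the analysis.

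**What to change.** In SAP 9.8.5:
1. Add a baseline-by-post-baseline cross-tabulation for ADA and for nAb.
2. Add treatment-induced ADA and nAb: negative at baseline, any positive sample afterwards. The denominator is baseline-negative subjects with at least one determinant post-baseline sample.
3. If titers are available, add treatment-boosted ADA with a titer-rise rule fixed in advance. If they are not, declare the omission in Section 10 with the reason.
4. Add a by-subject display of ADA status against trough concentration, citrulline, injection site reactions and hypersensitivity events. This delivers the impact description. It would also tie in the unscheduled ADA samples that the footnotes to Protocol Table 1 allow after an injection site reaction or hypersensitivity event.

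If the note to file, the shells or the PK/PD document already cover any of this, a cross-reference from 9.8.5 is enough for that part.

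The cost is small. Baseline and repeated post-baseline ADA samples are already scheduled, so items 1, 2 and 4 need only extra output and a few lines of text. Only item 3 depends on something the documents do not confirm.

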9.8.6 PK/PD

Descriptive statistics will be used to summarize the predose and post-dose apraglutide plasma concentrations and plasma citrulline levels by scheduled visit. All apraglutide plasma concentrations and plasma citrulline levels data will be listed.

Any exploratory PK analysis and PK/PD modelling will be described in a separate document.

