	
Safety assessments
 
• Colonoscopy* or colonography• Physical examination• Vital signs• Twelve-lead electrocardiogram• Body weight• Adverse events and AESIs• Concomitant medications• Clinical chemistry (including liver enzymes), hematology, and hemostasis• Anti-apraglutide antibodies and their neutralizing capacity (collectively ADA)• Urinalysis• Pregnancy test 
*Also performed for efficacy assessments

Trial product / intervention:	Apraglutide 2.5 mg or 5 mg SC once weekly
Control intervention (if applicable):	Not Applicable
Number of subjects with rationale:	This trial will enroll approximately 10 subjects. No formal sample size calculation has been performed for this trial. This number of subjects is considered sufficient to provide adequate information about the general safety, tolerability, efficacy, PD, and PK of the compound at this stage of development.
Trial duration:	Approximately 4 weeks of screening/baseline and 52 weeks on treatment, followed by a safety follow-up of 4 weeks (± 1 week).
Trial schedule:	First subject in is planned for approximately May 2021 Last subject in is planned for approximately May 2022 Last subject out is planned for approximately May 2023
Principal Investigator:	[REDACTED]
Trial centers:	Three European sites located in Belgium, Denmark, and France.
Statistical considerations:	Given the exploratory nature of the trial, the statistical evaluation will include mostly descriptive statistics and

Phase II Study of Apraglutide in SBS

	simple analysis contrasting 4 weeks, 24 weeks, 48 weeks, or 52 weeks against baseline or screening as appropriate.
GCP statement:	This trial will be conducted in compliance with the protocol, the current Declaration of Helsinki, International Council for Harmonisation-Good Clinical Practice (R2), as well as all national legal and regulatory requirements.

TRIAL SCHEDULE

Table 1: Schedule of Assessments (SoA)

	Screening	Baseline	Treatment Period												End of trial					
			1	2 ³	3	4	5 ³	6	7	8	9	10 ²⁶	11	12	13	14	15	16 ³	17	18
Visit No. ¹			-4 to -2 (Day -28 to -14)	-1 (Day -7 to -3)	0 (Day 0)	2 (+1)	4	8 ⁴ (±1)	12 (±2)	16 (±2)	20 (±2)	24 (±2)	28 (±2)	32 (±2)	36 (±2)	40 (±2)	44 (±1)	48 (±2)	52 (±2 days)	4 weeks after last dose ±1 week
Week (weeks unless indicated)																				
General																				
Informed consent	X																			
Inclusion and Exclusion criteria	X	X																		
Demographics	X																			

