7.4 Efficacy analysis

For all continuous efficacy endpoints mean change from baseline to end of treatment will be presented with simple 95% confidence interval and a t-test of no change from baseline. This will be done both for absolute and relative change. Due to the relatively small sample size, a non-parametric estimate of the change from baseline to end of treatment for each endpoint will be derived using the one-sample Hodges-Lehmann median estimator with corresponding 95% confidence interval.

As some of the continuous endpoints can be close to or below zero at baseline (e.g., absorption of energy), the relative change of such endpoints should be interpreted with great caution as the analysis can lead to meaningless results.

Responder endpoints will be tabulated with number of subjects and percentages of subject in FAS.

Other categorical endpoints will be tabulated with number of subjects and percentages of observed subjects. For ordinal endpoints change from baseline will also be calculated and tabulated.

For endpoints related to nutritional status and nutritional absorption sensitivity analyses will be made excluding subjects missing more than 20% of the planned

injections prior to the time of analysis. Hence the number of injections leading to exclusion will be one at Week 4, six at Week 24, and 11 at Week 52.

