3.2 SECONDARY OBJECTIVES

- To evaluate fluid, electrolytes, calories, and macronutrient absorption indicative of clinical efficacy (applicable to the protocol version 4)
- To evaluate fluid, electrolytes, and macronutrient absorption indicative of clinical efficacy (applicable to the protocol version 3)
- To evaluate the efficacy of apraglutide in reducing the administered volume per week of parenteral support (PS) from baseline
- To evaluate the safety and tolerability of apraglutide (applicable to the protocol version 3)
- To assess apraglutide plasma concentrations to inform the population pharmacokinetic (PopPK) model
- To evaluate citrulline plasma concentrations to inform the PopPK/Pharmacodynamic (PD) analysis

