7.2 SECONDARY ENDPOINTS

Efficacy endpoints related to PS volume

- Relative change from baseline in actual weekly PS volume at Weeks 4, 24 and 52
- Absolute change from baseline in actual weekly PS volume at Weeks 24 and 52
- Subjects who achieve a reduction of at least 1 day per week of PS from baseline at Weeks 24 and 52
- Clinical responders (20% reduction of PS volume from baseline) at Weeks 24 and 52
- Subjects reaching enteral autonomy at Weeks 24 and 52
- Energy reduction in the Parenteral Nutrition (PN) from baseline at Weeks 24 and 52

Efficacy endpoint related to nutritional, fluid (wet weight) and electrolyte absorption

- Absolute change in absorption of energy over MB periods from baseline to Week 48 (applicable to the protocol version 4)
- Relative change in absorption of energy over MB periods from baseline at Week 48
- Change in absorption of macronutrients over MB periods from baseline at Week 48

- Absolute change in absorption of energy over MB periods from baseline at Week 4
- Change in absorption of macronutrients over MB periods from baseline at Week 4
- Changes in urine output and urinary electrolytes (sodium, potassium, calcium and magnesium) over MB periods from baseline at Week 4 and at Week 48

Patient reported outcomes (PRO)

- Changes from baseline in [REDACTED] at Weeks 24 and 52
- Patient Global Impression of Change (PGIC) at Weeks 24 and 52
- Changes from baseline in Patient Global Impression of Treatment Satisfaction (PGI-TS) at Weeks 24 and 52
- Changes from baseline in Patient Global Impression of Satisfaction with PS (PGI-SPS) at Week 24 and 52
- Changes from baseline in Patient Global Impression of PS Impact (PGI-PSI) at Week 24 and 52.

PK/PD related endpoints

- Trough plasma concentration
- Plasma citrulline levels

Safety endpoints (applicable to the protocol version 3)

- AESI
- Clinical chemistry, hematology, hemostasis, ADAs, and urine analysis
- AEs

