9.2 DEFINITION OF BASELINE, TRIAL VISITS, AND VISIT WINDOWS

The baseline is the last available assessment/observation prior to first trial treatment (i.e. first administration of apraglutide). For assessments done on the same day as the first trial treatment, the time of assessment should be used to recognize whether or not the assessment was done prior to the first trial treatment. Otherwise, when the time of assessment is not available, last available assessments on or prior to the date of first trial treatment will be

considered as baseline since assessments are to be performed prior to dosing on the day of the first IMP administration according to the schedule of assessments in the protocol.

For evaluation of MB parameters, all relevant data measured over the MB period at the scheduled visit will be considered as the analysis timepoint. This applies to baseline, Week 4, and Week 48. The detailed derivation of baseline MB period data can be found in Section 9.7. Except for EOT visit data for efficacy analyses, by-visit efficacy data will be analyzed based on eCRF visits.

For all efficacy analyses, the EOT visit data will be mapped to a visit as defined below and will be only used to replace any missing by-visit efficacy data:

Table 9.2.1: Data Mapping Scheme

Visit	Analysis timepoint	Target day*	
4	Week 2	Day 15	
5	Week 4	Day 29	
6	Week 8	Day 57	
7	Week 12	Day 85	
8	Week 16	Day 113	
9	Week 20	Day 141	
10	Week 24	Day 169	
11	Week 28	Day 197	
12	Week 32	Day 225	
13	Week 36	Day 253	
14	Week 40	Day 281	
15	Week 44	Day 309	
16	Week 48	Day 337	
17	Week 52	Day 365	

*based on the relative days from the first trial treatment where the relative days from the first trial treatment = date of assessment or event – date of first trial treatment + 1, when both dates are known for assessments or events started on or after the day of the first trial treatment. (e.g., Relative Study Day 1 = the first study dosing day)

For safety data analysis, by-visit data will be analyzed based on the assigned analysis visit based on the data mapping scheme above. If more than one assessment falls into allowed time window the closest to the target date will be used. If two values are equidistant from the planned visit/assessment date, the first value will be used.

The citrulline and apraglutide plasma concentration data will be analyzed by scheduled visit based on eCRF visit (including EOT where applicable).

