9.8.3 LABORATORY DATA

For laboratory panels (hematology, chemistry, and hemostasis), summary statistics of observed and change from baseline values will be produced by analysis visit up to Week 52 for all continuous variables. For laboratory results reported with a prefix, for example "<" or ">", the value derived from the reported results without a prefix will be analyzed.

Shift tables will display the cross tabulation of Common Terminology Criteria for Adverse Events (CTCAE) grades (based on version 5.0 or higher) from the baseline to worst post-baseline based on the maximum post-baseline grade during the treatment and safety follow-up periods considering both scheduled and unscheduled post-baseline values. The percentages will be calculated based on the number of subjects assessed who have both baseline and post-baseline results.

All laboratory data for hematology & hemostasis, chemistry, urinalysis, endocrinology, and serology will be listed.

There will be separate listings for hematology & hemostasis, and chemistry data with clinically significant results.

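### SAP 9.8.6 summarises plasma citrulline, the only pharmacodynamic secondary endpoint, as levels by visit and specifies no within-subject change from baseline

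*SAP*

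**What the plan says.** SAP 7.2 lists "Plasma citrulline levels" as a secondary endpoint under the PK/PD heading, beside trough concentration. It names no change and no timepoint. The matching objective in SAP 3.2 is "To evaluate citrulline plasma concentrations to inform the PopPK/Pharmacodynamic (PD) analysis".

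The planned analysis, in SAP 9.8.6, is: "Descriptive statistics will be used to summarize the predose and post-dose apraglutide plasma concentrations and plasma citrulline levels by scheduled visit". The same section adds: "All apraglutide plasma concentrations and plasma citrulline levels data will be listed". It leaves PK/PD modelling to a separate document. SAP 9.2 ties the citrulline summary to scheduled eCRF visits, with the end-of-trial (EOT) visit included where it applies.

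SAP Appendix 1, Table 1, marks citrulline sampling at Visit 2 (baseline), at Weeks 2, 4, 12, 24, 32, 40, 48 and 52, and at EOT.

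For the haematology, chemistry and hemostasis panels, SAP 9.8.3 plans more: "summary statistics of observed and change from baseline values will be produced by analysis visit up to Week 52". SAP 9.8.4 does the same for vital signs, weight and ECG intervals. SAP 9.7 gives continuous efficacy endpoints a mean change with a 95% CI and a Hodges-Lehmann estimate with its CI. Citrulline does not appear in 9.7.2 or 9.7.3.

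**The concern.** Protocol 1.4 describes citrulline as a biomarker of small-intestine enterocyte mass, and protocol 1.8 uses citrulline increases in the dose rationale. In a single-arm trial, the natural question is how far each subject's citrulline moved from that subject's own pre-dose value, and how consistently. The SAP text plans no summary that answers this with a measure of spread. A named secondary endpoint is thus described less fully than a routine chemistry analyte.

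Two things are at stake:

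- **Precision.** Separate visit summaries do not contain the SD of the change, so no proper interval can be formed from the table.
- **Like-for-like comparison.** A visit mean can rise or fall because a different set of subjects was sampled. With 9 subjects, one absence removes 1/9 = 11% of a visit's data.

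**Working it through.** The documents state no figure for citrulline precision, so there is nothing to reproduce. The check has four steps.

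**1. Is a within-subject change planned anywhere?** SAP 9.1 derives absolute and relative change for efficacy parameters only. SAP 9.7 applies it to efficacy endpoints, and 9.8.3 and 9.8.4 apply it to laboratory panels, vital signs, weight and ECG. The passages on citrulline (SAP 7.2, 9.2, 9.8.6) name levels and listings only.

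**2. What does the level table show?** Baseline (Visit 2) is itself a scheduled citrulline visit, so it is one of the visits summarised. If the same n subjects are present at both visits, mean(follow-up) − mean(baseline) = mean(follow-up − baseline) exactly. Direction and average size are therefore visible. The SD of the change is not, because it depends on the within-subject correlation rho, which the visit summaries do not carry.

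**3. Precision.** Inputs: n = 9 (2 French and 7 Belgian subjects, SAP Introduction). Assumptions: equal SD at both visits, results in units of that SD, and rho from 0.3 to 0.9. The documents give no rho.

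- Two visit summaries treated as independent: t(2n−2) × sqrt(2/n) = 2.12 × 0.471 = 1.00
- Paired change: t(n−1) × sqrt(2(1−rho)/n), with t(8) = 2.306

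| rho | paired 95% half-width, n = 9 |
|---|---|
| 0.3 | 0.91 |
| 0.5 | 0.77 |
| 0.7 | 0.60 |
| 0.8 | 0.49 |
| 0.9 | 0.34 |

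With n = 8 the figures are 1.07 against 0.99 to 0.37. With n = 10 they are 0.94 against 0.85 to 0.32.

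**4. Can different subjects contribute to different visits?** Yes, by three routes in the SAP:

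- Subjects entering the extension trial have no EOT assessments (SAP 4.1), so the EOT row is a self-selected subset.
- Interim tables use whatever data exist at the snapshot (SAP 6), so visits after Week 4 at the first interim, or after Week 24 at the second, may hold only part of the cohort.
- Missing values are in general not replaced (SAP 9.3).

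For size, suppose 2 of 9 subjects lack the later sample and nobody's citrulline changes at all. The difference in visit means is then the mean of the remaining 7 minus the mean of all 9.

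- Missing at random: SD of the shift = sqrt(1/7 − 1/9) = 0.18 SD.
- The two lowest missing: average shift +0.35 SD (simulation from a normal distribution, 200,000 samples).

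A change computed only in subjects with both values would be zero in both cases.

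**The case against.** The strongest case on the other side has five parts.

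- **The output already shows a rise.** A reader might infer that the planned output cannot show whether citrulline rose. The documents do not support that: baseline is in the table, the difference in means equals the mean change for a common set of subjects, and every value is listed. With 9 subjects, individual changes can be worked out by hand. This stands. What remains is that a listing is not a summary and gives no interval.
- **The SAP analyses the endpoint as worded.** The endpoint is levels, and its objective is to feed the PopPK/PD work. This also stands. However, that modelling is described as exploratory and sits elsewhere, so it does not guarantee a summary of change.
- **The protocol does not clearly require more.** A reader might infer a breach from protocol 7.4 ("For all continuous efficacy endpoints mean change from baseline to end of treatment will be presented with simple 95% confidence interval") together with protocol 5.1.11.2, which places citrulline under an efficacy laboratory heading. A reader might also cite the synopsis ("simple analysis contrasting 4 weeks, 24 weeks, 48 weeks, or 52 weeks against baseline or screening as appropriate"). Neither settles it. The endpoint lists keep PK/PD apart from efficacy, the protocol treats PK/PD separately in 7.5, and the 5.1.11.2 heading also covers apraglutide concentration. Protocol 7.1 confines the added simple analyses to efficacy endpoints and patient-reported outcomes. The synopsis sentence begins by calling the evaluation mostly descriptive and ends with a qualifier.
- **The precision comparator is not a planned analysis.** True: the SAP plans no interval for citrulline. The 1.00 SD figure is only what a reader of the level table could construct, and the gain depends on an assumed rho. The documents also report no actual amount of missing citrulline data.
- **CIs and Hodges-Lehmann estimates go beyond what routine analytes get.** True. The change summary is the core of the remedy. The intervals borrow the SAP's own method for other secondary endpoints.

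**Conclusion.** The point holds as a gap in the analysis and its precision. SAP 9.8.6 specifies no within-subject change for citrulline, although the baseline sample is collected and the SAP summarises change for routine laboratory values. The level table gives direction and average size when the subjects are the same. It gives no spread or CI of the change, and it is open to shifts in who contributes.

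The size at n = 9 is a 95% half-width of 0.91 to 0.34 SD paired against 1.00 SD from separate summaries, and a spurious shift with an SD of 0.18 if 2 of 9 are missing at random. These figures rest on equal SDs, an assumed rho and, for the shift, an assumed pattern of absence.

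Three limits apply. No protocol departure is shown. The note to file of 6 December 2022 overrides the SAP text and table shells, and neither it nor the shells were available, so a change column may already exist. In a single-arm trial, even the paired result shows change on treatment, not an effect against control.

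**What to change.** In SAP 9.8.6, keep the table of levels and add:

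- absolute and relative change in citrulline from the last pre-dose value (normally Visit 2, following the baseline rule in SAP 9.2) at each scheduled visit, using subjects with both values and showing their number
- the mean change with 95% CI, and the Hodges-Lehmann estimate with 95% CI, at key visits, for example Weeks 4, 24, 48 and 52
- optionally, a line plot of individual values by visit.

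State that the EOT summary excludes subjects who entered the extension trial. Pairing removes the shift in composition, but not the selection in who attends. State also whether citrulline falls under the efficacy rule in SAP 9.7 or only under 9.8.6. First check the note to file and the table shells, in case they already provide for this.

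The cost is a few lines of SAP text and one table, plus a figure if wanted. No new samples or visits are needed.
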